1053 While very rare, participants treated with Empagliflozin may present with pain or tenderness, 1054 erythema, or swelling in the genital or perineal area, along with fever or malaise, and should be 1055 assessed for necrotizing fasciitis. If suspected, the study team will assess and refer the participant 1056 for appropriate care. Empagliflozin will be discontinued and blood glucose levels will be closely 1057 monitored, and provide appropriate alternative therapy for glycemic control. The study physician 1058 will contact the participant's personal physician.

1059 **12.3 General Considerations**

1060 The study is being conducted in compliance with the policies described in the study policies 1061 document, with the ethical principles that have their origin in the Declaration of Helsinki, with 1062 the protocol described herein, and with the standards of Good Clinical Practice (GCP).

- 1063 Whenever possible, data will be directly collected in electronic case report forms, which will be1064 considered the source data.
- 1065 The protocol is considered a significant risk device study, due to the fact that the closed loop 1066 system is experimental. Therefore, an investigational device exemption (IDE) from the U.S. Food 1067 and Drug Administration (FDA) is required to conduct the study.

1068 Chapter 13 Adverse Events, Device Issues, and Stopping Rules

1069 **13.1 Definitions**

1070 **13.1.1 Adverse Events (AE)**

1071 Any untoward medical occurrence in a study participant, irrespective of the relationship between 1072 the adverse event, the study drug, and the device(s) under investigation (section 13.2) for 1073 reportable adverse events for this protocol). Pregnancy will not be considered an adverse event.

1074 **13.1.2 Serious Adverse Event (SAE)**

- 1075 Any untoward medical occurrence that:
- 1076 Results in death.
- 1077 Is life-threatening; (a non-life-threatening event which, had it been more severe, might have
- 1078 become life-threatening, is not necessarily considered a serious adverse event).
- 1079 Requires inpatient hospitalization or prolongation of existing hospitalization.
- 1080 Results in persistent or significant disability/incapacity or substantial disruption of the ability to1081 conduct normal life functions (life threatening).
- 1082 Is a congenital anomaly or birth defect.
- 1083 Is considered a significant medical event by the investigator based on medical judgment (e.g.,

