- 1084 may jeopardize the participant or may require medical/surgical intervention to prevent one1085 of the outcomes listed above).

1086 **13.1.3 Unanticipated Adverse Device Effect (UADE)**

Any serious adverse effect on health or safety or any life-threatening problem or death caused by, or associated with, a device, if that effect, problem, or death was not previously identified in nature, severity, or degree of incidence in the investigational plan or application (including a supplementary plan or application), or any other unanticipated serious problem associated with a device that relates to the rights, safety, or welfare of participants (21 CFR 812.3(s)).

1092 13.1.4 Adverse Device Effect (ADE)

Any untoward medical occurrence in a study participant which the device may have caused or towhich the device may have contributed.

1095 **13.1.5 Device Complaints and Malfunctions**

1096 A device complication or complaint is something that happens to a device or related to device 1097 performance, whereas an adverse event happens to a participant. A device complaint may occur 1098 independently from an AE, or along with an AE. An AE may occur without a device complaint or

1099 there may be an AE related to a device complaint. A device malfunction is any failure of a device

- to meet its performance specifications or otherwise perform as intended. Performancespecifications include all claims made in the labeling for the device. The intended performance
- 1102 of a device refers to the intended use for which the device is labeled or marketed. (21 CFR 803.3).

1103 **13.2 Reportable Events**

- 1104 For this protocol, a reportable adverse event includes any untoward medical occurrence that 1105 meets one of the following criteria:
- 1106 A serious adverse event as defined in section 13.1.2
- An Adverse Device Effect as defined in section 13.1.4, unless excluded from reporting in section13.7
- 1109 An Adverse Event as defined in section 13.1.4 occurring in association with a study procedure
- 1110 An AE as defined in section 13.1.1 which leads to discontinuation of a study device for 2 or 1111 more hours
- 1112 Hypoglycemia meeting the definition of severe hypoglycemia as defined in section 13.2.1
- 1113 Diabetic ketoacidosis (DKA) as defined in section 13.2.2 or in the absence of DKA, a
- 1114 hyperglycemic or ketosis event meeting the criteria defined below

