- 1148 other means—will be reported on an adverse event form online. Each adverse event form is
- 1149 reviewed by a Study Physician to verify the coding and the reporting that is required.
- 1150 **13.3 Relationship of Adverse Event to Study Device**
- 1151 The study investigator will assess the relationship of any adverse event to be related or unrelated
- 1152 by determining if there is a reasonable possibility that the adverse event may have been caused
- 1153 by the study device.
- 1154 To ensure consistency of adverse event causality assessments, investigators should apply the 1155 following general guideline when determining whether an adverse event is related:
- 1156 There is a plausible temporal relationship between the onset of the adverse event and the
- 1157 study intervention, and the adverse event cannot be readily explained by the participant's
- clinical state, intercurrent illness, or concomitant therapies; and/or the adverse event follows
- a known pattern of response to the study intervention; and/or the adverse event abates or
- resolves upon discontinuation of the study intervention or dose reduction and, if applicable,
- 1161 reappears upon re-challenge.
- 1162 Evidence exists that the adverse event has an etiology other than the study intervention (e.g.,
- 1163 preexisting medical condition, underlying disease, intercurrent illness, or concomitant
- 1164 medication); and/or the adverse event has no plausible temporal relationship to study 1165 intervention.

1166 **13.4 Intensity of Adverse Event**

The intensity of an adverse event will be rated on a three-point scale: (1) mild, (2) moderate, or
(3) severe. It is emphasized that the term severe is a measure of intensity: thus, a severe adverse
event is not necessarily serious. For example, itching for several days may be rated as severe,

1170 but may not be clinically serious.

- 1171 MILD: Usually transient, requires no special treatment, and does not interfere with the 1172 participant's daily activities.
- 1173 MODERATE: Usually causes a low level of inconvenience or concern to the participant and may 1174 interfere with daily activities, but is usually ameliorated by simple therapeutic measures.
- 1175 SEVERE: Interrupts a participant's usual daily activities and generally requires systemic drug
- therapy or other treatment.

1177 **13.5 Coding of Adverse Events**

- 1178 Adverse events will be coded per the UVA IRB website instructions (i.e. mild, moderate, severe).

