- Handling of Missing Data: All randomized participants who have at least 50% of their CGM readings during the study period will be included in the analysis. Occasional missing CGM data do occur during normal CGM use and these values will be ignored when summary CGM metrics (e.g. percent times in range, LBGI, HBGI) are computed. Typically, CGM data are voluminous and the percent of missing values is low; thus no imputation would be required. For example, in the recently completed multi-center Protocol 3 of the International Diabetes Closed Loop Trial, N=168 subjects (of N=168 recruited) completed the entire 6-month protocol, and CGM data were
- 1335 available 96% of the time [15] (Table 1).
- 1336 Safety outcomes will be reported for all enrolled participants, irrespective of whether the 1337 subjects were randomized or the study was completed.
- 1338 Data Analysis: The objectives of this study are addressed by different sub-analyses of our general
 1339 analytical scheme, as follows:
- 1340Objective 1: Effect of adding Empagliflozin to predictive low glucose suspend (Basal IQ 21341weeks) and closed-loop control (Control IQ 4 weeks) will be assessed by the study1342randomized design (Figure 1). In this design we will have N=20 participants on Empagliflozin1343and N=20 participants off Empagliflozin, beginning with Control IQ and then switching to1344Basal IQ, or beginning with Basal IQ and then switching to Control IQ. This analysis will be1345done using the baseline data as covariates in a general linear model.
- 1346Objective 2: CGM-measured effect of Empagliflozin will be assessed using the baseline CGM1347data, (between Visits 2 and 3) via direct contrast between the two Experimental and two1348Control groups (N=20 participants in Groups 1-2 vs 20 participants in Groups 3-4);
- 1349Objective 3: CGM-measured effects of Empagliflozin added to Basal IQ will be assessed by1350direct comparison of the Experimental vs Control groups during the Basal IQ sessions (N=201351participants per arm will be available to this analysis);
- 1352Objective 4: CGM-measured effects of Empagliflozin added to Control IQ will be assessed1353by direct comparison of the Experimental vs Control groups during the Control IQ sessions1354(N=20 participants per arm will be available to this analysis);

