CGM use during the study			97%	96%		
Percent below 70 mg/dL	3.59 ± 3.39%	2.82 ± 2.53%	1.59 ± 1.15%	2.25 ± 1.46%	-0.88%	<0.0001
Percent 70-180 mg/dL (study primary outcome)	60 ± 17%	59 ± 14%	71 ± 12%	59 ± 15%	+11%	<0.0001
Percent above 180 mg/dL	36 ± 19%	38 ± 15%	27 ± 12%	39 ± 15%	-10%	<0.0001

Percent above 250 mg/dL	12.4 ± 12.8%	11.9 ± 9.9%	7.0 ± 6.7%	12.4 ± 10.3%	-5.5%	<0.0001
HbA _{1c}	7.4%	7.4%	7.06%	7.4%	-0.33%	=0.0014
Mean glucose [mg/dL]	166 ± 32	169 ± 25	156 ± 19	170 ± 25	-13	<0.0001
Coefficient of Variation	37 ± 6%	36 ± 5%	34 ± 5%	36 ± 5%	-3%	<0.0001

1379 Overall, the studies using the AP algorithm originally developed at the University of Virginia, have

1380 logged >65,000 days of use to date, in 31 clinical trials enrolling over 600 children and adults with

1381 type 1 diabetes at 15 clinical centers in the U.S. and Europe (Table 1). Control IQ is the third

1382 commercial-grade generation of this algorithm, which will be used in this study.

1383 **15.3 Outcome Measures**

1384 **15.3.1 Primary Efficacy Endpoint**

To demonstrate the efficacy of Empagliflozin as adjuvant therapy added to a closed loop artificial pancreas system (AP-EMPA) in patients with T1DM. The primary efficacy outcome variable will be time in range (70-180 mg/dl). Secondary efficacy outcomes will be: time below 70 mg/dl, time above 180 mg/dl, time between 70-140 mg/dl 5 hours postprandial, glucose variability indices (HBGI, LBGI, ADRR). The corresponding variables obtained from the NO-AP-EMPA arm will be the comparator.

1391 **15.3.2 Secondary Outcome**

- 1392 To evaluate the safety of Empagliflozin as adjuvant therapy added to a closed loop artificial
- 1393 pancreas system (AP-EMPA) in subjects with T1DM by monitoring:
- 1394 Episodes of diabetic ketoacidosis (DKA)
- 1395 Episodes of severe hypoglycemia (glucose <50 mg/dl)
- 1396 Genital infections (balanitis, urethritis, vulvar infections, Fournier's gangrene)
- 1397 Urinary tract infections
- 1398 Other AE CGM based LBGI & HBGI
- 1399 Furthermore, we will compute
- 1400 Total amount of insulin used
- 1401 Number of hyperglycemic episodes as defined by contiguous CGM above 300mg/dL

1402 **15.4 Safety Analyses**

1403 All randomized participants will be included in these analyses and the circumstances of all 1404 reportable cases of the following will be summarized and tabulated by treatment group:

- 1405 Severe hypoglycemia
- 1406 Diabetic ketoacidosis

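### DKA and severe hypoglycemia each have two conflicting definitions, 13.3 asks for no separate drug-relatedness judgement, and non-serious genital or urinary infections have no explicit reporting rule

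*Combined protocol and SAP*

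**What the plan says.** **DKA.** Section 8.3 gives the DSMB three rates to weigh when considering whether to stop: mild ketosis (B-OH-B above 0.6 mmol) over 40%, significant ketosis (above 1.5) at 20%, and DKA (above 3) over 5%. No symptom is required. Section 13.2.2 classifies a hyperglycemic event as DKA when there are symptoms and serum ketones are at least 1.5 mmol/L or urine ketones are large or moderate. It lists ketones of 3.0 mmol/L or more as a separate reportable criterion.

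**Severe hypoglycemia.** Section 15.3.2 uses glucose below 50 mg/dl. Section 13.2.1 uses need for another person's help or cognitive impairment, with no glucose cut-off.

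**Relatedness.** Section 13.1.1 defines an adverse event irrespective of the relationship between "the adverse event, the study drug, and the device(s) under investigation (section 13.2) for" the list of reportable events. The question in 13.3 concerns the study device only. Section 13.9.1 treats a DKA attributable to the drug differently from one that is not. In 8.3, continuation while DSMB review is pending depends on there being no serious events related to the drug.

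**Infections.** Section 15.3.2 lists "Genital infections (balanitis, urethritis, vulvar infections" and Fournier's gangrene) and urinary tract infections as safety outcomes. Section 15.1 says that safety outcomes "will be reported for all enrolled participants, irrespective of whether the" participant was randomized or completed. Section 13.2.2 says that reportable events "will be reported on an adverse event form online". Section 13.2 begins "For this protocol, a reportable adverse event includes any untoward medical occurrence that" meets one of its criteria. Section 15.4 tabulates reportable cases on four lines.

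**The concern.** Safety of the drug combined with closed loop is half of the stated purpose. If two sections attach the same label to different events, the count depends on which section the person classifying the event had open. For DKA that count feeds a limit at which the DSMB is to consider stopping. For severe hypoglycemia it is a listed safety outcome.

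Rules that turn on whether the drug caused an event also need that judgement to be made and recorded. The only relatedness question in the protocol is about the device.

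Finally, section 12.2.1 names urinary and genital mycotic infections as the most recognized reactions to the drug. An ordinary, non-serious case has no clear route from the clinic contact to an adverse event form and then to a table.

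**Working it through.** The plan states no figure to reproduce here. The check compares sections and then counts.

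**1. DKA: which events change class.** All examples are hyperglycemic events.

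| Event | 8.3 | 13.2.2 |
|---|---|---|
| Symptomatic, ketones 2.0 mmol/L | significant ketosis, not DKA | DKA |
| Asymptomatic, ketones 3.2 mmol/L | DKA | not DKA (reportable as ketones of 3.0 or more) |
| Symptomatic, ketones above 3 mmol/L | DKA | DKA |

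The first two rows are discordant and the third is not.

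**2. What one discordant event does to the 5% limit.** Section 8.3 gives no denominator, so the following are assumptions. The rate is 1/n under the definition that counts the event and 0/n under the other.
- n = 10 (the participants at the review): 1/10 = 10% against 0%.
- n = 5 (roughly those on drug among the 10, at 1:1): 1/5 = 20% against 0%.
- n = 19: 1/19 = 5.3%, still over 5%.
- n = 20: 1/20 = 5.0%, not over 5%.

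So a single event crosses the limit for any denominator up to 19.

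**3. Singly or jointly.** Section 8.3 joins the three limits with a bare conjunction. At n = 10, counting everyone above each cut-off:
- over 40% needs 5 participants (4/10 = 40% is not over);
- over 20% needs 3 (2/10 = 20% is not over), or 2 if that limit means at least 20%;
- over 5% needs 1.

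If the limits act singly, one DKA is enough. If they act jointly, at least 5 participants above 0.6, 3 above 1.5 (or 2) and 1 DKA are all required. A discordant event then matters only when the other two limits are also exceeded.

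**4. How likely such an event is.** The documents give no rate. With an assumed per-participant probability p, the chance of at least one event among 10 is 1 − (1 − p)^10: 9.6% at p = 1%, 18.3% at 2%, 40.1% at 5% and 65.1% at 10%. These are illustrations of scale, not estimates.

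**5. Severe hypoglycemia.** A self-treated episode at 48 mg/dl is severe under 15.3.2 only. An assisted episode at 52 mg/dl is severe under 13.2.1 only. Section 13.9.1 cites 13.2.1, and 15.4 uses reportable cases, so the conflict is confined to the 15.3.2 outcome.

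**6. Relatedness.** Section 13.3 is headed for the device and asks about the device. Its guideline mentions the study intervention, dose reduction and re-challenge, which could take in the drug, but it sets no separate drug judgement. At-occurrence DSMB review (8.3, 13.10) covers all DKA and severe hypoglycemia. For other events it covers only serious ones related to the device. Section 13.9.2 separately pauses the study to discuss certain severe events with the DSMB once two subjects have had them.

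**7. Infections against the six criteria in 13.2.**
- Serious event: only if serious, including the route "Is considered a significant medical event by the investigator based on medical judgment" in 13.1.2.
- Adverse device effect: not a drug reaction.
- "An Adverse Event as defined in section 13.1.4 occurring in association with a study procedure": 13.1.4 defines device effects. If that is a slip for 13.1.1, taking the drug would still have to count as a study procedure.
- An event "which leads to discontinuation of a study device for 2 or" more hours: concerns stopping a device, not the drug.
- Severe hypoglycemia, and DKA or another hyperglycemic or ketosis event: do not apply.

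None of the six names the drug. Of the four specific clinical events in 15.3.2, DKA and severe hypoglycemia each have a 13.2 criterion and a 15.4 line. Genital and urinary infections have neither, unless serious.

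**The case against.** **Infections.** A reader might infer that the plan would under-record these infections. The documents do not support that. Section 15.3.2 commits to monitoring them and 15.1 to reporting safety outcomes. The opening of 13.2 is inclusive, not a closed list. Its express exclusions from recording concern glucose events and sensor skin reactions. Sections 13.4 and 13.6 expect mild and continuing events in the record. What stands is narrower: no rule requires a form for a non-serious infection, and 15.4 has no line for one, so recording could be incomplete.

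A reader might also infer that counts cannot be compared between arms, because 9.1.1 and 9.4 mention drug effects only for the Empagliflozin group. But 9.1.1 is a condition for continuing after run-in, 9.4 contacts all participants, and adverse events are reviewed in both arms under the visit schedule and 9.10. Unequal ascertainment is a minor possibility and not a finding.

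**Relatedness.** It is tempting to say that drug causality is never assessed. The 13.3 guideline can be read to cover the drug, 13.5 records the investigator's and the DSMB's causality assessments, and the adverse event form is not among the documents. What stands is that the protocol specifies no separate drug judgement although two of its rules use one.

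**DKA.** Section 8.3 guides a board on rates, whereas 13.2.2 classifies individual events, and the board decides on the totality of safety data. It would therefore be too strong to say that the definition alone decides whether the trial stops. Every event classed as DKA also goes to the DSMB at occurrence, and the separate DSMB document named in 13.10 may say more. Yet both sections call the event DKA, and neither says that the difference is intended.

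**Conclusion.** The concern holds as an internal inconsistency that should be fixed. The heaviest part is DKA. One discordant event exceeds the 5% limit under one definition and contributes nothing under the other, provided that the 8.3 limits act singly and the denominator is 19 or fewer. Both conditions are assumptions, because 8.3 states neither. If the limits act jointly, the effect is confined to cases where the two ketosis limits are also exceeded.

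The severe hypoglycemia conflict is certain from the text but affects one listed outcome. The missing drug-relatedness judgement matters because 8.3 and 13.9.1 rely on it, and because serious drug-related events other than DKA and severe hypoglycemia are outside at-occurrence DSMB review, apart from the two-subject pause in 13.9.2. The infection gap is the least of the four. Nothing here touches the primary endpoint or the sample size, and no view is taken on which clinical definition is right.

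**What to change.** - **Definitions (8.3, 13.2.1, 13.2.2, 15.3.2).** The sponsor and DSMB should reconcile the two DKA definitions and the two severe hypoglycemia definitions, or give them different names if both are wanted.
- **8.3 limits.** State the denominator and whether the three limits act singly or jointly.
- **13.3.** Record relatedness to the drug and to the device as two separate judgements.
- **8.3 and 13.10.** Include drug-related serious events in at-occurrence DSMB review.
- **13.2 and 15.4.** Make genital and urinary infections reportable, ask about them at the same contacts in both arms, and tabulate them by arm. Check the reference to 13.1.4 in the study-procedure criterion.

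The cost is protocol wording, a few CRF fields and some extra adverse event forms at one site.
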